**Table 2 List of Laboratory Tests**

Hematology:	Serum Chemistry:
- Complete blood count (CBC)	- Albumin (ALB)
Urinalysis:	- Alkaline phosphatase (AP)
- Protein	- Alanine aminotransferase (ALT; SGPT)
- Glucose	- Aspartate aminotransferase (AST; SGOT)
- Bilirubin	- Blood urea nitrogen (BUN)
- pH	- Calcium (Ca)
- Nitrite	- Carbon dioxide (CO 2 )
- Ketones	- Chloride (Cl)
- Urobilinogen	- Creatinine
- Occult blood	- Creatine kinase
- Leukocyte esterase	- Gamma-glutamyl transferase (GGT)
Microscopic examination for blood, all types of cells and casts.	- Globulin
Serum and urine human chorionic gonadotropin (hCG) (only for females who have reached menarche)	- Glucose
HLA DQB1:0602 haplotype (at Part 1 Screening only, for subjects with no previous documented results available)	- Lactate dehydrogenase (LDH)
Tests of growth and precocious puberty:	- Phosphorus
- Growth hormone (GH)	- Potassium (K)
- Insulin-like growth factor-1 (IGF-1, low sensitivity)	- Sodium (Na)
- Prolactin	- Total bilirubin
- Luteinizing hormone (LH)	- Direct bilirubin
- Follicle Stimulating Hormone (FSH)	- Total cholesterol
- Testosterone	- Total protein
- Estradiol	- Triglycerides
	- Uric acid
	Coagulation (within 30 days prior to PK Night 1 for PK subjects only):
	- Prothrombin time (PT)/International normalized ratio (INR)
	- Activated partial thromboplastin time (PTT)
	Thyroid Function
	- Thyroid stimulating hormone (TSH) (at Part 1 Screening only)

The clinical laboratory tests will be performed at a central or local laboratory. An authorized back-up laboratory, as indicated on the Form FDA 1572 or equivalent, may be used if necessary as an emergency laboratory. The Investigator will supply Jazz Pharmaceuticals or its designee with the back-up laboratory's current licensure and laboratory reference ranges.

Please note exclusionary clinical laboratory parameters listed in the exclusion criteria. In addition, any laboratory parameter that is out of range and considered clinically significant (as determined by the Investigator) at the end of treatment must be re-evaluated. The

Xyrem® (sodium oxybate) oral solution  
Clinical Study Protocol: 13-005 Amendment 5

Jazz Pharmaceuticals

---

Investigator will provide an explanation of all clinically significant observations. These findings will be reported as AEs.

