**Table 3 Estimated Blood Volumes for Assays in Part 1 – Non-PK Subjects**

	Screening (Day -30 to -1) a	End of Stable- Dose (Week 3 – Week 10)	End of Double- Blind (Week 5 – Week 12)	Termination (Part 1 Early Termination or Week 52)	Total
Clinical chemistry	7.5 mL	--	7.5 mL	7.5 mL	22.5 mL
TSH		--	--	--	
hCG		--	Included in Chemistry	--	
Girls <8 years old: LH, FSH, estradiol Boys <9 years old: LH, FSH, testosterone		--	--	Included in Chemistry	
Hematology	2 mL	--	2 mL	2 mL	6 mL
HLA DBQ1 602	3 mL	--	--	--	3 mL
GH, prolactin	--	3.5 mL	Included in Chemistry	Included in Chemistry	3.5 mL
IGF-1	--	3.5 mL	3.5 mL	3.5 mL	10.5 mL
Approximate total blood volume per subject	12.5 mL	7 mL	13 mL	13 mL	45.5 mL

a If needed, additional screening time may be granted with permission of the Medical Monitor.

Estimated blood volumes for subjects who are participating in the PK evaluation are listed in [Table 4](#). The approximate total blood volume to be collected for study assessments in these subjects is 88.2 mL over a period of one year.

Xyrem® (sodium oxybate) oral solution  
Clinical Study Protocol: 13-005 Amendment 5

Jazz Pharmaceuticals

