- Confirm the subject has been on a stable dose of Xyrem for the previous 2 months. Confirm the subject has been on a stable dose of stimulants, if applicable, for the previous 2 months. Record the subject's prescribed usual dose and regimen of Xyrem and stimulants if applicable.
- Perform a physical examination, including a brief neurological examination and a Tanner Stage Assessment ([Appendix 5](#)) but excluding a full genitourinary exam.
- Record height and weight in ordinary indoor clothes (without shoes).
- Administer the following and record results:
  - ESS (CHAD) ([Appendix 6](#))
  - Columbia-Suicide Severity Rating Scale (C-SSRS) ([Appendix 8](#));  
Baseline/Screening version for subjects  $\geq 12$  years of age and Children's  
Baseline/Screening version for subjects  $< 12$  years of age)

- 
- Children’s Depression Inventory 2nd Edition Self-Report Short Version ([Appendix 9](#))
  - Multi-dimensional Anxiety Scale for Children (MASC-10) ([Appendix 10](#))
  - Obtain vital signs (systolic and diastolic blood pressure, pulse/heart and respiratory rate, and body temperature) after the subject has been resting for at least 5 minutes.
  - Obtain pulse oximetry reading on room air while the subject is fully awake.
  - Obtain blood samples for the following:
    - Routine hematology, chemistry, and thyroid function (see [Table 2](#))
    - Serum pregnancy test (only for female subjects who have reached menarche)
    - For PK subjects only: coagulation (PT/INR and PTT)
    - HLA DQB1:0602 (if the subject has no previous HLA DQB1:0602 result available and no documented CSF hypocretin level  $\leq 110$  pg/mL)
    - For girls <8 years of age: estradiol, FSH, and LH
    - For boys <9 years of age: testosterone, FSH, and LH
  - Obtain urine samples for urinalysis.
  - Perform alcohol test and urine drug screens.
  - Obtain a 12-lead ECG.
  - Schedule Screening PSG
  - Subjects will continue dosing with their own supply of Xyrem during the Screening Period, with the exception of the Screening PSG Night when Xyrem will be provided.
  - Instruct subjects or parent(s)/guardian(s) on how to complete the Dosing Diaries (Study Drug Dosing Diary in [Appendix 12](#) and Stimulant Dosing Diary in [Appendix 13](#)).

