#### 7.1.4 End of Stable-Dose Period/Beginning of the Double-Blind Treatment Period\*, Subjects on Xyrem at Study Entry (Visit 3, Week 3 ±3 days)

\*Subjects entering the Double-Blind Treatment Period after Amendment 4 becoming effective will complete this visit and receive open-label Xyrem during this period.

- Collect a fasting blood sample for GH, IGF-1, and prolactin.
- Provide breakfast for the subject after the fasting blood sample is collected.
- Record height and weight in ordinary indoor clothes (without shoes).
- Obtain vital signs (systolic and diastolic blood pressure, pulse/heart and respiratory rate, and body temperature) after the subject has been resting for at least 5 minutes.
- Review Cataplexy Frequency Diary.
- Review the Dosing Diaries for compliance with dosing.
- Complete CGIs for narcolepsy overall (current condition) ([Appendix 17](#)) and for cataplexy severity (current condition) ([Appendix 18](#)).
- Administer the following:
  - ESS (CHAD) ([Appendix 6](#))
  - SF-10 ([Appendix 7](#))
  - C-SSRS ([Appendix 8](#); Since Last Visit version for subjects ≥12 years of age and Children's Since Last Visit version for subjects <12 years of age)
  - CDI 2:SR[S] ([Appendix 9](#))
  - MASC-10 ([Appendix 10](#))
- Collect information on school attendance ([Appendix 14](#)) if the subject is currently attending school and will be attending school during the Double-Blind Treatment Period.

Xyrem® (sodium oxybate) oral solution  
Clinical Study Protocol: 13-005 Amendment 5

Jazz Pharmaceuticals

- Record all AEs on the AE CRF.
- Record all concomitant medications on the concomitant medications CRF.
- Dispense study drug. (Access IVRS/IWRS.) Provide instructions for dose administration and, if flavored diluent is requested and available, the preparation of study drug with flavored diluent to subjects/parent(s)/guardian(s). See [Section 6.10](#).
- Collect study drug dispensed at Visit 2 and assess compliance.
- Schedule next visit (Visit 4) in the morning, and inform subjects/parent(s)/guardian(s) that subjects must be fasting for IGF-1, GH, and prolactin testing when they arrive at the visit.

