#### 7.4.3 Visit 15 Week 52 or Part 1 Early Termination

If the subject will be continuing directly into Part 2, the Open-Label Continuation Period, see [Section 7.5](#).

- Perform a physical examination, including a brief neurological examination and a Tanner Stage Assessment ([Appendix 5](#)) but excluding a full genitourinary exam.
- Record height and weight in ordinary indoor clothes (without shoes).
- Review Cataplexy Frequency Diary.
- Review Study Drug Dosing Diary.
- Administer the following:
  - ESS (CHAD) ([Appendix 6](#))
  - SF-10 ([Appendix 7](#))
  - C-SSRS ([Appendix 8](#)) (Since Last Visit version for subjects  $\geq 12$  years of age and Children's Since Last Visit version for subjects  $< 12$  years of age)
  - CDI 2:SR[S] ([Appendix 9](#))
  - MASC-10 ([Appendix 10](#))
- Obtain vital signs (systolic and diastolic blood pressure, pulse/heart and respiratory rate, and body temperature) after the subject has been resting supine for at least 5 minutes.
- Obtain urine samples for urinalysis.
- Perform alcohol test and urine drug screens.
- Obtain urine sample for pregnancy test (only perform for female subjects who have reached menarche).
- Obtain a 12-lead ECG.
- Record all AEs on the AE CRF.
- Record all concomitant medications on the concomitant medications CRF.
- Collect study drug dispensed at the previous visit and measure compliance.
- Perform End of Study (Part 1) PSG according to the procedures for all subjects in Column 4 of [Table 6](#). If the subject withdraws early from the study during the Open-Label Safety Period, perform the PSG if subject is willing to be dosed with study drug

on this PSG night. Part 1 early termination PSG does not apply for subjects who discontinue before entering the Open-Label Safety Period.

- Obtain blood samples for the following the morning after the PSG night:
  - Fasting blood sample for GH, IGF-1, and prolactin
  - Routine hematology and chemistry
  - For girls <8 years of age: estradiol, FSH, and LH
  - For boys <9 years of age: testosterone, FSH, and LH
- If the subject will not be continuing into Part 2, record the reason why and schedule the Safety Follow-up visit.

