Visits	V1 Day -30 to -1 a,b	V2 Day 1	V3 Week 3 ± 3 days	V4 Week 5 +3 days	V5 Week 9 ±7 days	V6 W 16 ±7 days Phone call	V7 W 18 ±7 days	V8 W 22 ±7 days Phone call	V9 W 26 ±7 days	V10 W 30 ±7 days Phone call	V11 W 34 ±7 days Phone call	V12 W 39 ±7 days	V13 W 43 ±7 days Phone call	V14 W 48 ±7 days Phone call	Visit 15 c W 52 ±7 days Or Part 1 Early Termination	V16 d 14 days after last treatment +3 days
Pulse Oximetry on room air while fully awake	X															
HLA DQB1:0602 f	X															
Hematology, Chemistry g	X			X											X	
TSH	X															
PK subjects only: Coagulation h	X i															
Urinalysis	X			X											X	
Only for Girls <8 years: estradiol, LH, FSH Only for Boys <9 years: testosterone, LH, FSH	X														X	
Urine Drug Screen	X	X		X j	X		X		X			X			X	
Alcohol Test	X	X		X j	X		X		X			X			X	
Serum Pregnancy	X			X												
Urine Pregnancy		X													X	
12-Lead ECG	X			X											X	

Xyrem® (sodium oxybate) oral solution  
 Clinical Study Protocol: 13-005 Amendment 5

Jazz Pharmaceuticals

**Appendix 1.1 Part 1 Screening, Stable-Dose Period, Double-Blind Treatment Period, Open-Label Safety Period—Subjects on Xyrem at Study Entry**

	Screening Visit	Start Stable-Dose	End Stable-Dose/ Begin Double-Blind Treatment*	End Double-Blind*/ Begin Open-Label Safety	Open-Label Safety Period with Xyrem											Safety Follow-up
					V5 Week 9 ±7 days	V6 W 16 ±7 days Phone call	V7 W 18 ±7 days	V8 W 22 ±7 days Phone call	V9 W 26 ±7 days	V10 W 30 ±7 days Phone call	V11 W 34 ±7 days Phone call	V12 W 39 ±7 days	V13 W 43 ±7 days Phone call	V14 W 48 ±7 days Phone call	Visit 15 c W 52 ±7 days Or Part 1 Early Termination	
Visits	V1 Day -30 to -1 a,b	V2 Day 1	V3 Week 3 ± 3 days	V4 Week 5 +3 days	V5 Week 9 ±7 days	V6 W 16 ±7 days Phone call	V7 W 18 ±7 days	V8 W 22 ±7 days Phone call	V9 W 26 ±7 days	V10 W 30 ±7 days Phone call	V11 W 34 ±7 days Phone call	V12 W 39 ±7 days	V13 W 43 ±7 days Phone call	V14 W 48 ±7 days Phone call	Visit 15 c W 52 ±7 days Or Part 1 Early Termination	V16 d 14 days after last treatment +3 days
Cataplexy Frequency Diary k																
CGIs for Historical Narcolepsy Overall Severity Prior to any Narcolepsy Treatment	X 															

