	Screening Visit	Start Stable-Dose	End Stable-Dose/ Begin Double-Blind Treatment*	End Double-Blind*/ Begin Open-Label Safety	Open-Label Safety Period with Xyrem											Safety Follow-up
					V5 Week 9 ±7 days	V6 W 16 ±7 days Phone call	V7 W 18 ±7 days	V8 W 22 ±7 days Phone call	V9 W 26 ±7 days	V10 W 30 ±7 days Phone call	V11 W 34 ±7 days Phone call	V12 W 39 ±7 days	V13 W 43 ±7 days Phone call	V14 W 48 ±7 days Phone call	Visit 15 c W 52 ±7 days Or Part 1 Early Termination	
Visits	V1 Day -30 to -1 a,b	V2 Day 1	V3 Week 3 ± 3 days	V4 Week 5 +3 days	V5 Week 9 ±7 days	V6 W 16 ±7 days Phone call	V7 W 18 ±7 days	V8 W 22 ±7 days Phone call	V9 W 26 ±7 days	V10 W 30 ±7 days Phone call	V11 W 34 ±7 days Phone call	V12 W 39 ±7 days	V13 W 43 ±7 days Phone call	V14 W 48 ±7 days Phone call	Visit 15 c W 52 ±7 days Or Part 1 Early Termination	V16 d 14 days after last treatment +3 days
Dispense Study Drug o		X	X	X	X		X		X			X				
Collect study drug, measure compliance			X	X	X		X		X			X			X	
Fasting morning blood sample: GH, IGF-1, prolactin			X	X											See Appendix 1.2 P	
Breakfast			X	X											See Appendix 1.2 P	
PSG	See Appendix 1.2														See Appendix 1.2 P	
PK subjects only: PK Nights 1 and 2		When the subject is on a stable dose of Xyrem, PK Nights 1 and 2 can be scheduled for a protocol-specified clinic visit or for an additional clinic visit. See Appendix 3														

An arrow (  ) indicates that the assessment is continuous.

\* **Subjects who enter the Double-Blind Period after Amendment 4 becoming effective will receive open-label Xyrem during the Double-Blind Period.**

- a) All subjects will provide their written informed consent prior to the performance of any study-related procedures. The Screening Visit (Visit 1) starts when a subject is assigned a subject number via IVRS/IWRS. If needed, additional screening time may be granted with permission of the

Xyrem® (sodium oxybate) oral solution  
Clinical Study Protocol: 13-005 Amendment 5

Jazz Pharmaceuticals

---

Medical Monitor.

- b) The Screening Period for subjects with low body weight who are participating in the PK evaluation should be as close as possible to 30 days to minimize the amount of blood drawn over 30 days.
- c) If the subject is continuing directly into Part 2, see [Appendix 22](#).

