## Appendix 1.2 PSG Night Procedures– Subjects on Xyrem at Study Entry

	Part 1 Screening Visit	Open-Label Safety Period with Xyrem
Visits	V1 Day -30 to -1 a	Visit 15 Week 52 (±7 days) Or Part 1 Early Termination
PSG Night Proceduresb	Screening PSG	End of Study (Part 1) PSG /Part 1 Early Termination
Review inclusion/exclusion criteria	X	
Light dinner >2 hours before dosing	X c	X c
Confirm Parent(s)/ Guardian(s) Contact Information	X	X
Administer or supervise the administration of Study Drug d	X	X
PSG	X	X e
EtCO 2 or TcCO 2 f	X	X
Vital Signs g	X	X
Pulse Oximetry h	X	X
Record AEs/Concomitant Medications	X	X
Brief neurological exam i	X	X
Fasting morning blood sample : GH, IGF-1, prolactin		X
Breakfast (if subject prefers to eat at the study center)	X	X

- a) If needed, additional screening time may be granted with permission of the Medical Monitor.
- b) Perform all other procedures for the visit prior to the PSG night procedures.
- c) Light dinner taken >2 hours prior to dosing. The dinner should be the same or similar on all PSG nights and may be taken at the Sleep Lab or home.
- d) Administer the subject's nightly dose of Xyrem divided in two doses, at bedtime and 4 hours later while in bed.
- e) Part 1 Early termination PSG does not apply for subjects who discontinue before entering the Open-Label Safety Period.
- f) CO2 monitoring on PSG nights only at sites where monitoring is routinely performed.
- g) Obtain vital signs (blood pressure, pulse/heart rate, body temperature, respiratory rate) after subject has been resting for ≥5 min. Obtain at pre-dose and before release from study center. At 1, 4 (pre-2nd dose), 5, and 8 hours after the 1st Xyrem dose, heart and respiratory rates recorded via PSG.
- h) SpO2 monitored continuously from immediately before first dose through 8 hours post-first dose, and recorded pre-dose and at 1 h, 2 h, 4 h (pre-2nd dose), 5 h, 6 h, and 8 h after the first dose. Additional measurement is taken while the subject is awake and before release from the study center.
- i) Brief neurological exam before discharge on the morning after PSG.

Xyrem® (sodium oxybate) oral solution  
Clinical Study Protocol: 13-005 Amendment 5

Jazz Pharmaceuticals

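### Screening chemistry has no fasting requirement, while Visit 4 and Visit 15 chemistry shares the fasting morning sample, so changes from Screening in glucose and triglycerides can carry a fed-to-fasted shift

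*Protocol*

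**What the plan says.** **Panel and visits.** Table 2 places glucose, total cholesterol and "Triglycerides" in serum chemistry. The row "Hematology, Chemistry" in Appendix 1.1 is marked in Part 1 only at Visit 1 (Screening), Visit 4 and Visit 15. Appendices 2.1 and 2.2 give the same three visits for Xyrem-naïve subjects. The separate Appendix 1.1 row "Fasting morning blood sample: GH, IGF-1, prolactin" is filled at Visits 3 and 4 and, by reference to Appendix 1.2, at Visit 15; it is blank at Screening.

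**Screening.** Section 7.1.1 lists "Routine hematology, chemistry, and thyroid function", and Section 7.2.1 does the same for naïve subjects. Neither mentions fasting or a time of day. Table 6 specifies no blood draw after the Screening PSG in either cohort.

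**Visit 4.** Section 7.1.4 tells sites: "Schedule next visit (Visit 4) in the morning, and inform subjects/parent(s)/guardian(s) that subjects must be fasting for IGF-1, GH, and prolactin testing". Section 7.2.4 gives naïve subjects an equivalent instruction. Sections 7.1.5 and 7.2.5 put the fasting hormones and routine chemistry in one sampling step, with breakfast afterwards.

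**Visit 15.** Sections 7.4.3 and 7.5.1 say: "Obtain blood samples for the following the morning after the PSG night". The list that follows holds both the fasting hormones and routine chemistry, and Table 6, column 4, agrees. Section 5.8.2 allows no food between the light dinner and the next morning.

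**Blood volumes.** Tables 3 and 4 enter GH and prolactin at Visits 4 and 15 as "Included in Chemistry".

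**Order of procedures on PSG visits.** Note b of Appendices 1.2 and 2.3 reads: "Perform all other procedures for the visit prior to the PSG night procedures". The PSG-night lists in those appendices contain the fasting hormone sample but not chemistry.

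**The concern.** The protocol controls fasting at both on-study chemistry visits of Part 1 and leaves it open at the only earlier one. In Xyrem-naïve subjects the Screening value is the only chemistry before treatment, so any change attributed to starting Xyrem has to be measured from it.

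Eating raises glucose and triglycerides. If some children were fed at Screening and all are fasted later, the average change is pushed downwards. A real rise on Xyrem could be hidden, or a fall could appear where there is none. More subjects would not average this out. Out-of-range counts at Screening and on treatment would also stop being like for like.

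One-year safety is Primary Objective 2, and the change to Visit 15 has no concurrent control. Weight loss is on the DSMB list in Section 9.9, and Section 1 names obesity as a comorbidity, so metabolic laboratory values are of some interest. That link is an inference, since the protocol sets no glucose or lipid endpoint.

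**Working it through.** **Step 1. Is the Visit 4 and Visit 15 chemistry really the fasting sample?** Table 3 can be used as a check. Its inputs are chemistry 7.5 mL, hematology 2 mL, HLA 3 mL, GH with prolactin 3.5 mL where separately drawn, and IGF-1 3.5 mL.

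- Screening: 7.5 + 2 + 3 = 12.5 mL
- Visit 3: 3.5 + 3.5 = 7 mL
- Visit 4: 7.5 + 2 + 3.5 = 13 mL
- Visit 15: 7.5 + 2 + 3.5 = 13 mL
- Total: 12.5 + 7 + 13 + 13 = 45.5 mL, the plan's own figure

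If GH and prolactin had their own 3.5 mL at Visits 4 and 15, each visit would need 13 + 3.5 = 16.5 mL and the total would be 12.5 + 7 + 16.5 + 16.5 = 52.5 mL. That does not match. The chemistry sample at those visits therefore supplies the fasting hormones and is itself fasting.

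**Step 2. Could the Screening sample be fasting by another route?** An overnight stay would do it, but Table 6 has no draw after the Screening PSG. The visit text gives no instruction. On the protocol's text, fasting status at Screening is uncontrolled.

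**Step 3. Form of the artefact.** Let f be the share of children who had eaten before the Screening draw, and d the mean fed-minus-fasted difference in SDs of the change. With later samples all fasting, the spurious mean change is −f × d. Neither input is in the protocol. The ranges below are assumptions that only show how the artefact scales.

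| f | d = 0.2 | d = 0.5 | d = 1.0 |
|---|---|---|---|
| 0 | 0 | 0 | 0 |
| 0.25 | −0.05 SD | −0.125 SD | −0.25 SD |
| 0.5 | −0.10 SD | −0.25 SD | −0.50 SD |
| 1 | −0.20 SD | −0.50 SD | −1.00 SD |

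With one fasting condition at all three visits the term becomes 0 for any d.

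**Step 4. Which comparisons carry it?**

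- Naïve subjects, Screening to Visit 4 or Visit 15: yes, with no control to remove it.
- Subjects on Xyrem at entry: the shift is present, but they already take the drug at Screening, so their change is not a drug-onset effect.
- Randomized Xyrem versus placebo at Visit 4: both arms have the same Screening and Visit 4 conditions, so the term cancels on average.
- Efficacy endpoints: none uses chemistry.

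**Step 5. Visit 15 timing.** Chemistry is not on the PSG-night lists of Appendices 1.2 and 2.3. Read literally, note b therefore moves it before the PSG night, when no fasting is required. Sections 7.4.3 and 7.5.1 and Table 6 place it on the fasting morning after. Under note b, GH and prolactin could no longer share the chemistry sample. Visit 15 would then need 16.5 mL and the Table 3 total would be 45.5 + 3.5 = 49.0 mL, against the stated 45.5 mL.

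**The case against.** The best counter-argument is that silence is not evidence. A reader might infer that Screening samples are taken from fed children. The protocol does not say so. It sets no rule, and Section 6.9.2.1 refers to detailed laboratory instructions that are not shown and might contain one. This stands, and it is why the finding concerns a missing requirement and why f runs from 0.

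A reader might also be tempted to express the shift as several standard errors of the mean change. That needs every one of 100 children to have been fed, all of them to reach Visit 15, and outside figures for the fed-fasted difference and its spread. It also implies a test nobody planned. The documents do not support it.

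It is fair to add that Section 9.9 plans only descriptive safety summaries, that no laboratory baseline is named, and that such definitions usually belong in the analysis plan. This lowers the weight of the point without removing it. Whatever baseline is chosen, no chemistry value before Visit 4 exists except the one at Screening.

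On Visit 15, the specific sections and Table 6 outnumber one general footnote, and most sites would probably follow them. If note b were followed instead, the mismatch between Screening and Visit 15 would shrink and one between Visits 4 and 15 would open. The texts still need to agree.

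Not every later value is fasting either. Subjects who stop before the Open-Label Safety Period have no termination PSG, so the timing of their termination draw is not fixed by it. Part 2 Screening chemistry (Section 7.6.1) also carries no fasting rule.

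**Conclusion.** The point holds in limited form. The protocol's own text and blood-volume arithmetic show that Part 1 chemistry is fasting at Visits 4 and 15 and uncontrolled at Screening. Changes from Screening in glucose and triglycerides can therefore be biased downwards, in proportion to the unknown share of children who had eaten. The conclusion assumes that no fasting rule sits in the unseen laboratory instructions and that sites follow Sections 7.4.3 and 7.5.1 for Visit 15.

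The size cannot be computed from the documents. It could be nil if all children happened to be fasted at Screening. The weight falls on the uncontrolled changes to Visits 4 and 15 in Xyrem-naïve subjects. This is a safety-data issue affecting a few analytes, and it is worth correcting because the remedy is cheap. The contradiction over Visit 15 timing needs no assumption and should be resolved in any case.

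**What to change.** 1. Apply the fasting-morning instruction already used for Visits 3 and 4 to the Screening chemistry draw (Sections 7.1.1 and 7.2.1 and both schedules) for any child still to be screened. Few may remain: the original protocol dates from April 2014, Part 1 enrollment was expected to take 2 years, and Amendment 5 is from February 2017.
2. Record fasting status with every chemistry sample. For past Screening samples, retrieve it where possible. Otherwise, footnote the tables to say that fasting at Screening was uncontrolled.
3. Summarize glucose and triglycerides by fasting status.
4. Reconcile note b of Appendices 1.2 and 2.3 with Sections 7.4.3 and 7.5.1 and Table 6, so that Visit 15 chemistry is drawn with the fasting sample.
5. If a fasting-to-fasting comparison is wanted, show the change from Visit 4 to Visit 15 as a supplement, by treatment received in the Double-Blind Period. It should not replace the change from Screening. Naïve subjects may reach Visit 4 as late as about Week 14, so any earlier drug effect is already in that reference, and placebo subjects are off drug at that visit.

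The cost is a fasting morning draw at Screening for children not yet screened, one field on the laboratory form, a footnote, and a wording correction in two appendices.
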